Clinicians will be [name], BA, [name], MA, LPC, [name], MSW, LCSW, [name], MA, LPC and [name], MA. [name], [name], [name] and [name] are all licenced therapists in the St. Louis community and [name] is a PhD clinical psychology graduate student in the Department of Psychology at Washington University. All clinicians have been intensively trained in RO DBT. Group skills classes will be run by both the PI, [name], [name] and/or another clinician. Paper notes will be kept in a locked file cabinet in locked offices. De-identified therapy notes will be uploaded to a secure Wustl box.com folder for the study. At the end of therapy, the clinician will complete an “End of Therapy Progress” questionnaire to assess progress made or not made across the research study. In addition, the participant will be contacted via phone call and asked several questions about their experience with RO DBT along with their perceptions of treatment outcomes. In addition, research team member will contact subjects who have dropped out of the study or who have completed treatment. The participant will be contacted via phone call to and invited to participate in a follow up interview. They will be asked several questions about their experience with

Ketamine enhanced RO DBT along with their perceptions of treatment outcomes. This will be conducted over zoom and be recorded or over the phone and audio recorded to a handheld recorder. The recording will be immediately transferred to a wustl box, in a secured password protected account. The data from the recording will be deleted immediately from the handheld recorder. At the end of the study a research team member will transcribe the recordings and save the transcriptions to a wustl box folder. All audio and video recordings will be deleted at that time.

G Statistical Plan

G1 Sample Size Determination and Power

Using G*Power, power for Aim 1 (MDD symptoms) was based on a) a pilot of RODBT from the PI, b) Lynch et al. (2020),⁽⁹⁾ a multi-site RCT of RODBT in TRD and c) Zarate et al (2006)⁽³⁷⁾, an original RCT of ketamine in TRD. With $\alpha=.05$ and power of 80%, we would need a sample of 8 to detect an effect from RODBT, and $n=5$ with ketamine. For Aim 2, we used a) Baudinet et al (2021)⁽¹¹⁾ who tested RODBT change in behavioral flexibility and reward processing and b) a pilot of RODBT from the PI. With $\alpha=.05$ and power of 80%, we would need a sample of 5-15 participants to detect behavioral change in mechanistic process. Power for neural change in HPM/OC has not been computed because no previous studies have targeted HPM/OC with ketamine. However, our sample is similar to other medication-assisted psychotherapy pilot studies.

G2 Interim Monitoring and Early Stopping

This is part of Analysis 1a below. Specifically, side effects and symptoms will be monitored at each ketamine and RO DBT session for 4 weeks while they are running concurrently. If there are any issues with running a ketamine session and a psychotherapy session within 1-2 days of each other, protocols can be modified or stopped, if necessary.

G3 Analysis Plan

Analysis 1a: No analyses will be completed for H1a; qualitative data from session questionnaires regarding side-effects, symptoms and functioning will be continually monitored, to assess if there is a need to modify protocols. **H1b:** Using individual session data, ketamine will catalyze psychiatric symptom change in RODBT and ketamine-enhanced RODBT will be associated with decreasing trajectories of depressive symptoms. Analysis 1b: Multilevel linear modeling (MLM) with random intercepts and slopes will model trajectories of depressive symptoms across treatment.

Aim 2: Examine preliminary efficacy of ketamine-enhanced RODBT in engaging neural and behavioral mechanistic targets in young adults with

moderate to severe depression.

H2a: Ketamine-enhanced RODBT will be associated with neural ERN reductions and neural RewP increases. Analysis 2a: Using baseline, mid- and post-treatment assessments, change in the ERN (and in a separate model, the RewP) will be assessed using a MLM. **H2b:** Ketamine-enhanced RODBT will be associated with behavioral cognitive flexibility, openness, reward responding and social functioning improvements. Analysis 2b: Using baseline, mid- and post-treatment assessments, change in behavioral mechanisms will, similar to Analysis 2a, be assessed using a MLM.

G4 Statistical Methods

See above

G5 Missing Outcome Data

If missing outcome data exists, that participant will be excluded for that analysis. Of note, when modeling data, missing data does not mean the participant can be excluded.

H References

1. Lynch TR. Radically Open dialectical behavior therapy: Theory and practice for treating disorders of overcontrol. Oakland, CA: Context Press; 2018.

-

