facilitating change in RODBT. Ketamine has demonstrated change in neural reward responding and has improved social functioning in depression,(18) both of which are central to the HPM/OC phenotype. Indeed, work from key personnel on this proposal demonstrate that in adults with TRD, ketamine infusions demonstrate response-dependent changes in functional connectivity in the anterior cingulate cortex (ACC), default mode network and limbic/reward structures, including the amygdala and nucleus accumbens.(19) Of note, the ACC has been repeatedly implicated in performance and error-monitoring (e.g., HPM/OC),(20) and is where the EEG-based neural marker, the ERN is thought to originate(21) while the nucleus accumbens is a reward structure where the RewP is theorized to originate from.(22) Together, ketamine may provide initial, fast-acting change to catalyze and facilitate longer-term neural and psychiatric change in RODBT in individuals with TRD. Ketamine-assisted psychotherapy is still in early stages of study,(18) so the current proposal will take a 'deep-dive' examination of feasibility and session-by-session change in ketamine- enhanced RODBT. This will allow us to a) test whether ketamine acts as a catalyst to RODBT, increasing openness and flexibility for RODBT therapy sessions and b) examine trajectories of change across the treatment, assessing when ketamine induced plasticity is associated with the largest drop in psychiatric symptoms (Aim 1). Additionally, repeated EEG neural assessments (baseline, post-ketamine and post-RODBT) will allow us to a) test whether a shorter course of RODBT, boosted with concurrent ketamine (8 weeks) is enough to enact neural change, or, whether the full course of ROBDT (16 weeks) is necessary to elicit neural change and b) assess whether targeting the neural and behavioral mechanism of HPM/OC is directly associated with improving MDD symptoms and functioning (Aim 2).

B2 Rationale for this Study

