The experimental research measures in this project will not directly benefit the participants, other than the knowledge that they are contributing to our understanding of the underlying factors that may cause treatment-resistance to previous treatments and may provide insight into a novel medication-enhanced psychotherapy and thus, there is a benefit of contribution to society. In the therapy portion of the project, it is also possible that participants may experience improved symptoms of depression, mood, anxiety, as well as reduced tendencies of HPM/OC. As part of the ketamine treatment, participants may also experience improved symptoms of depression and anxiety. There is a possible effect that the combination of ketamine and RO DBT will be especially beneficial in combination, although this is unknown, as it is a goal of the study to test the combined treatment. As mentioned above, measures are being taken to minimize any potential risks.

E Study Design

E1 Overview or Design Summary

Eligible patient (n=15) young adults will attend a baseline session where they will undergo an ERP neural assessment and fill out questionnaires. Then, participants will complete 4 weeks of ketamine and 4 months of RO DBT. Participants will start with 2 weeks of individual therapy (RODBT) to orient to therapy and infusion protocols. Then, participants will complete a 4-week course of twice weekly 40-minute ketamine infusions administered 6-24 hours prior to RO DBT psychotherapy (also when RO DBT group therapy will commence). Following completion of the 4-week ketamine-enhanced RO DBT, participants will complete another in-person session with an EEG and behavioral assessment. Next, participants will continue to complete RO DBT treatment of individual and group treatment for an additional 16 weeks. At the end of this treatment, participants will complete a third session where they will undergo an ERP neural assessment and fill out questionnaires. Participants will also complete self-reported questionnaires following each ketamine and RO DBT

session (4 weeks) and weekly self-reported questionnaires during non-ketamine RO DBT.

E2 Subject Selection and Withdrawal

2.a Inclusion Criteria

Young adults with treatment-resistant depression: Inclusion criteria:

- Males and females aged 18-65

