Re: Therapy and ketamine trial-- Participants are not randomized. They will be fully informed of the free therapy and ketamine trial and will not be coerced into it. Free therapy and ketamine will be provided to all patients (as this is a feasibility and acceptability study). If any patient participating in the study needs a higher level of care, they will immediately be removed from the treatment protocol and will be coordinated with other providers to ensure they get the care necessary. If any patient participating in the study decides they no longer want to be in the trial, they can end at any point and it will be coordinated to help them continue treatment with other providers.

Re: experimental session—all participation is voluntary, including answering questions and participating in the ERP.

2.c Subject Recruitment Plans and Consent Process

Study population:

Young adults age 18-65 years with TRD who exhibit HPM/OC.

Consent process: If an interested participant contacts the research team about the study, a member of the research team will provide information about the study and required elements of consent over the telephone (see attached “Consent for Phone Screen”) prior to obtaining the participants verbal consent to participate in the screening elements of the study. This phone screen will allow possible participants to ask questions and clarifications prior to coming in person for the in-person consent process (and includes the child having the opportunity to ask questions). If a participant meets eligibility criteria for enrollment in the study based on their Initial Phone/Exclusion Screen and the participant indicates they wish to continue with the study, the participant will receive an email to complete the a measure of HPM/OC, the Word Pairs Checklist. The participant must consent to complete these questionnaires. If the participant is eligible following completion of the phone screen and questionnaires, the research team will notify the participant of their eligibility and ask whether they want to continue with the study. If the participant is unsure, the research assistant will provide

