way) to 4 (almost always respond in this way) scale that assesses emotion regulation specifically during positive emotional experiences. The RPA has three factor-derived subscales, including Emotion-focused and Self-focused positive rumination and Dampening, which assesses ways positive emotion might be diminished (e.g., “Think about things that could go wrong”). The two positive rumination subscales are often studied in the context of bipolar disorder and are associated with elevated manic symptoms, while elevated dampening has been associated with both current and predictive depressive symptoms in both mood disordered (bipolar and depressed) and non-clinical populations (Johnson, McKenzie & McMurrich, 2008). In the current study we are using the Dampening eight item subscale only. Ask Suicide-Screening Questions (ASQ)- The ASQ is a brief (5 questions) assessment to gauge suicide risk in participants. OC Trait Rating Scale – This scale assesses maladaptive aspects of the HPM/OC 'overcontrolled phenotype' that we will use to assess whether ketamine and RO DBT are targeting the mechanistic processes inherent in the overcontrolled phenotype.

Ketamine session questionnaires:

In addition to completing the above mentioned PHQ-9 and GAD-7 at each ketamine infusion, participants will also complete:

Brief Psychiatric Rating Scale- positive (psychotic) symptoms subscale (BPRS+): This measures transient neuropsychiatric changes that might occur in response to the ketamine infusions. KetRO Clinical Events Checklist: This measure assesses common adverse side effects of using ketamine. Clinical Administered Dissociative State Scale (CADSS) – Modified – This measure assesses dissociative symptoms after using ketamine.

Before the ketamine administration, participants will have vital signs collected in addition to and ECG and blood chemistry tests.

During the ketamine + RO DBT portion of the study, participants will also complete the PHQ-9 and GAD-7 following each RO DBT session. Following completion of the ketamine portion, and ongoing weekly RO DBT therapy, participants will complete the PHQ-9 and GAD-7 weekly following their individual therapy sessions.

At the end of treatment, participants will be asked to complete a post-treatment questionnaire. The participants' therapists will also be asked to complete a separate end of therapy questionnaire.

Visit 2 etc.

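### Aim 1 asks when symptoms fall most, but Analysis 1b has no term that can answer, and reading the timing from observed session means would be unreliable for small steps

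*Combined protocol and SAP*

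**What the plan says.** The timing question appears in section B1 (Prior Literature and Studies). As one of two uses of the session-by-session data, the team will "examine trajectories of change across the treatment, assessing when ketamine induced plasticity is associated with the largest drop in psychiatric symptoms (Aim 1"). The sentence is tagged to Aim 1. The question is not repeated in the hypotheses (A2), the primary aim (C1) or the analysis plan (G3), where H1b speaks only of ketamine catalysing change and of decreasing trajectories.

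For H1b, G3 gives one sentence: "Multilevel linear modeling (MLM) with random intercepts and slopes will model trajectories of depressive symptoms across treatment". It states no coding of time, phase or session contrast, change-point, reference for a maximum, or interval for a timing.

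The study has one arm: "Eligible patient (n=15) young adults will attend a baseline session" (E1), and "Participants are not randomized" (E2, Ethical Considerations). On the schedule, E1 says "Participants will start with 2 weeks of individual therapy (RODBT) to orient to therapy and infusion protocols", and then "participants will complete a 4-week course of twice weekly 40-minute ketamine infusions". PHQ-9 forms are frequent. F2 introduces the infusion-day measures with "In addition to completing the above mentioned PHQ-9 and GAD-7 at each ketamine infusion", and asks for the form again after each therapy session in the ketamine phase and weekly afterwards.

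**The concern.** The largest of a series of changes always exists. Asking when it occurred presupposes a distinct moment, so the question needs an analysis that can also answer that there was none. Analysis 1b does not supply one. That leaves the method to be chosen after the data are seen, and the simplest choice is to look along the plotted session means for the steepest fall. The size of a fall selected that way is inflated by the selection, and its position is unstable unless one step is large relative to the noise in the means.

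At stake is the interpretation of the session-level look at the data, which B1 presents as a main feature of the study. A chance maximum could be described as the point at which ketamine-induced plasticity took effect. F2 lists no session-level measure of plasticity, and there is no comparison arm against which to judge timing.

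**Working it through.** **1. What the model estimates.** With linear time, Analysis 1b is y_ij = (b0 + u0_i) + (b1 + u1_i)·t_ij + e_ij. The modelled change between two times is (b1 + u1_i) × (elapsed time), so the rate is the same in every interval. No session or week can have the steepest fall. Categorical or piecewise time would change this, but G3 mentions neither.

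**2. How many intervals.**
- Ketamine phase: 2 infusions × 4 weeks = 8 forms, plus (1 individual + 1 group session) × 4 weeks = 8 forms, giving 16.
- Before ketamine: 1 baseline form plus 2 lead-in forms (weekly completion in the lead-in is assumed).
- After ketamine: 16 − 2 − 4 = 10 weekly forms if therapy lasts about 16 weeks in all (section F, Therapy), or 16 if it runs a further 16 weeks (E1).
- Total: 3 + 16 + 10 = 29 forms (28 intervals), or 3 + 16 + 16 = 35 forms (34 intervals).

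**3. The plan's own figures.** The documents give none for timing. The Aim 1 sample sizes in G1 (8 and 5) concern detecting an overall effect. Without the effect sizes they cannot be reproduced. At 80% power and two-sided 5% they imply standardised changes of 1.16 and 1.68.

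**4. Largest fall with no true change.** Stable differences between people cancel in consecutive changes. For within-person SD s and lag correlation r, the SD of the change in the mean of 15 people is s·√(2(1 − r)/15). The documents give neither s nor r. I assume s = 2 to 4 PHQ-9 points and r = 0 to 0.6 (first-order autoregressive).
- s = 2, r = 0.6: 2·√(0.8/15) = 0.46.
- s = 4, r = 0: 4·√(2/15) = 1.46.

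In simulation the largest fall averages roughly 1.8 of these SDs over 16 forms and 2.1 over 32:

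| Forms | Mean largest fall, no true change |
|---|---|
| 16 | 0.8 to 2.6 points |
| 32 | 1.0 to 3.0 points |

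A smooth trend does not remove the problem. With a steady 8-point decline over 28 intervals (8/28 = 0.29 per interval), s = 3 and r = 0, the largest observed fall averages 2.5 points although no interval is special.

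**5. How often a real step is found.** One step is added at one interval, with r = 0.3 and s = 2 to 4. A pure guess is right 1 time in 15 (7%) with 16 forms and 1 in 31 (3%) with 32.

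| True step | 16 forms | 32 forms |
|---|---|---|
| 1 point | 21-48% | 13-36% |
| 2 points | 46-90% | 35-86% |
| 3 points | 72-99% | 64-99% |
| 4 points | 90-100% | 85-100% |

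With independent noise the rates are lower. At s = 4, a 4-point step is found in 74% of trials over 28 intervals and 72% over 34.

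**6. If the selected fall were also tested.** The plan does not say it would be. With no change and independent noise, the largest fall passes an unadjusted two-sided 5% paired t-test in about 30% of trials over 16 intervals, 44% over 28 and 48% over 34. At least one interval shows a nominally significant fall in 34%, 52% and 58%. The independence formula 1 − (1 − 0.025)^K gives 33%, 51% and 58%. The one-directional 5% critical t for the largest fall is about 3.2, 3.5 and 3.6, against 2.14 for a single two-sided test on 14 df.

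**The case against.** The strongest reply is that this is one phrase in the background. It is absent from A2, C1 and G3, and the documents call the work preliminary and a feasibility and acceptability study. A reader might infer that the plan states a rule to pick the session with the largest observed fall and report it as when ketamine worked, so that a positive finding is guaranteed under no effect. The documents do not support that. No section says an observed maximum will be selected, tested or reported, and B1's question could refer to a week or a phase as well as a session. The planned H1b analysis is of trajectories, where no change means an expected slope of zero. Nor does any section say the timing would be used to schedule later treatment.

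It is also fair that noise does not always dominate. Even a 1-point step is located several times more often than by guessing, and a large abrupt fall would usually be placed correctly.

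These points limit the finding without removing it. B1 assigns the question to Aim 1, the session data are collected partly to answer it, and the plan provides no estimand, no measure of uncertainty and no exploratory label for it.

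**Conclusion.** The concern holds as a mismatch between a stated Aim 1 question and its analysis. With linear time, Analysis 1b cannot say when the fall was largest, nor that no moment stands out. That part rests only on the model as described and on the unstated time coding.

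The size of the risk is conditional on the timing being read from observed means. It then depends on the assumed within-person SD and lag correlation: the null largest fall scales with the SD, and stronger correlation shrinks it. Noise matters most when change is nil, gradual or a step of about 1 to 2 points. It matters much less for abrupt falls of 4 points or more.

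Even a correctly located fall could not be attributed to ketamine-induced plasticity, because plasticity is not measured by session and there is no control arm. The point is worth acting on because the repair is cheap, but it is not evidence that the plan will report noise as an effect.

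**What to change.** - In Analysis 1b, state the coding of time and replace the open timing question with fixed quantities: mean PHQ-9 change over each of the 4 ketamine weeks and over named later blocks, from categorical or piecewise time in the multilevel model.
- Give simultaneous 95% intervals suited to 15 participants, for example from a max-t reference. Percentile bootstrap intervals run narrow here: one nominal 95% interval behaves like ±1.96·√(14/15) = ±1.89 on a t scale with 14 df, which covers about 92%.
- If the timing of steepest change is still shown, label it exploratory and present its distribution from resampling participants, so that an indistinct answer is visible.
- Do not attribute the timing to ketamine-induced plasticity, in B1 or in reports.
- Reconcile the two therapy durations (E1 and section F, Therapy) before naming the later blocks, since they change the number of occasions.

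The cost is protocol and analysis-plan wording plus some programming. No visit, form or participant changes. The downside is weekly rather than session-level resolution, which merges the two infusions of each week. Session-level plots can stay as description.

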The outcome measures of neural and behavioral HPM/OC and neural reward and social responding have been chosen to assess the purported underlying mechanisms of change contributing to symptom presentations. We also included functioning and psychiatric symptoms to assess whether targeting a mechanism also influences symptom presentation.

D Investigational Agent

D1 Dose Rationale and Risk/Benefits

Details of Infusion

To ensure dose accuracy, participants will have weight confirmed prior to each infusion. All female participants will complete a urine pregnancy test immediately prior to their first ketamine infusion and will be informed that it is not advised to have unprotected sex throughout the ketamine infusion period (1 month). After safety ratings (see table below) are performed, an IV line will be inserted into upper extremity by research personnel. The ketamine will be infused using an IV infusion pump at a rate of 0.5 mg/kg of body weight over 40 minutes. Heart rate, blood pressure, and pulse-oximetry will be routinely monitored throughout the infusion and for approximately up to two hours after the end of the infusion. Safety ratings will be repeated prior to discharge. After normalization of any psychotomimetic symptoms or blood pressure elevation and IV removal, participants will be discharged.

Direct physical or psychological risks are minimal in the administration of behavioral and electrophysiological measures. Individual psychosocial therapy sessions can elicit some psychological distress while group sessions can elicit some psychological distress or social anxiety. Behavioral tasks can lead to some concern of performance or frustration. Additionally, participants may become bored or tired during the experimental sessions. Some mild discomfort may be associated with the application of the miniature surface electrodes and when skin is mildly abraded. At no time will subjects be coerced to participate in any aspect of testing, subjects will be told that at any time they wish to terminate the experiment or therapy, they are free to do so. There is also always a risk of loss of confidentiality; although this risk is minimal given data are stored electronically behind Washington University's firewall. Lastly, there is a risk of time burden.

Risks of Ketamine infusion:

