Subject confidentiality will be assured through a multi-layered approach, entirely compliant with HIPAA regulations. First, all demographic and other identifying information will be stored under at least two locks/passwords (in a password protected document on a password protected computer in a locked office or in a locked cabinet in a locked office). The participants' name and study number will be stored in a master file that contains no other demographic or research information. This master file will be a password protected document and stored on a password-protected computer. All other non-identifying information will only be assigned an ID and will also be protected under two locks/passwords. Only [name] and designees will have access to this information. Under no circumstances will individually identifiable data be released to anyone without written consent of the subject. Any data analyses and publications from this study will not individually identify participants and will focus on grouped data. The research data (including clinical adolescent and caregiver-reported assessments) will be examined as it is collected to review any clinical implication of the information. If any incidental findings are uncovered or clinical attention warranted at any point during study participation, this will be immediately

discussed with the principal investigator ([name]), a licensed clinical psychologist, and this information will be discussed with participants. Similarly, research study therapists will have weekly ongoing supervision and consultation meetings to discuss therapy cases. If increased clinical attention is warranted at any point during the four-month therapy, this will be immediately discussed with the PI and, if needed, the participant will be stepped up to a higher level of care.

Benefits:

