 - Moderate to severe persistent depression [treatment resistant depression – TRD] (exhibiting 2+ unipolar major depression episodes (non-delusional) with prior treatment non-response to antidepressant or psychosocial treatment
 - Treatment-resistant depression: defined as unipolar major depressive disorder, that persists despite ≥ 2 adequate antidepressant trials of different classes in the current episode; including at least one evidence-based second-line treatment in the current episode (including serotonin norepinephrine reuptake inhibitors, bupropion, tricyclics, monoamine oxidase inhibitors, or augmentation with an atypical antipsychotic, stimulant, bupropion, lithium, or Triiodothyronine)
 - higher proportion of OC words endorsed compared to UC words on the Word Pairs Checklist
 - no current or past psychosis
 - English speaking
 - Able to attend in-person behavioral sessions and ketamine/therapy visits
 - Willingness to have RO DBT as only psychosocial treatment engaged in (medication treatment may continue—but see below for exclusion)

2.a Exclusion Criteria

Exclusion criteria:

- Outside age range
- Significant neurological condition (i.e., seizure, stroke, severe head injury) or mental retardation (IQ<70)
- Current or recent substance use disorder, actively suicidal or homicidal (e.g., requires hospitalization)
- Use of naltrexone, memantine or medication considered contraindicated with ketamine
- Baseline systolic BP > 150 systolic or 90 diastolic at evaluation. Participants who initially present with elevated blood pressure may be re-assessed; and if needed, referred to their healthcare provider for hypertension management

-
- Taking more than 2 adequately-dosed oral antidepressants
 - Inability to understand, speak and read English sufficiently
 - Not be pregnant or at risk of becoming pregnant
 - Medical conditions or medication usage that in the judgement of the investigators puts the patient at unreasonable safety risk
 - First degree relative with a psychotic diagnosis involving hallucinations, delusions, or disorganized thinking and speech (e.g. schizophrenia, schizoaffective disorder, etc)

2.b Ethical Considerations

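### The only stated pregnancy test comes before infusion 1 of 8, with no repeat scheduled and no stated action if pregnancy is found mid-course

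*Combined protocol and SAP*

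**What the plan says.** **Testing and advice (D1, Details of Infusion).** "All female participants will complete a urine pregnancy test immediately prior to their first ketamine infusion". The same sentence has these participants told that "it is not advised to have unprotected sex throughout the ketamine infusion period (1 month". By contrast, the sentence before it repeats another check at every visit: "participants will have weight confirmed prior to each infusion".

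**Course length (E1).** Participants receive "a 4-week course of twice weekly 40-minute ketamine infusions", after two weeks of individual therapy.

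**Eligibility (E2, 2.a).** The trial takes "Males and females aged 18-65". The exclusion list contains the item "Not be pregnant or at risk of becoming pregnant". It also has a general medical item: "Medical conditions or medication usage that in the judgement of the investigators puts the patient at unreasonable safety risk".

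**Other checks.** Visit 1 (F2) lists a blood draw and an EKG. The checks before ketamine (F2, ketamine session questionnaires) are vital signs, an ECG and blood chemistry. Neither list names a pregnancy test, and the ketamine protocol later in section F names none.

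**What happens if a problem appears.** D1 sends clinical findings to the principal investigator and the participant ("If any incidental findings are uncovered or clinical attention warranted at any point during study participation"). E2, 2.d and 2.e allow withdrawal for medical or psychological instability, active suicidal ideation or the participant's own wish. G2 monitors side effects and symptoms at each session and allows the protocol to be modified or stopped if ketamine and therapy cannot be run close together. None of these names pregnancy.

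**The concern.** The plan treats pregnancy as a reason not to give ketamine: it is an eligibility matter, it is tested for before the first dose, and participants are warned for the whole infusion month. That month-long warning also shows that the plan expects some participants to be able to conceive while being dosed. Yet the only stated test is tied to the first infusion.

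Two situations are not covered: a pregnancy too early to show on the first test, and one that begins during the course despite screening and advice. In either case the participant could go on receiving infusions with no stated check. If the pregnancy did come to light, staff would have no written instruction to stop ketamine. At stake is participant safety.

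**Working it through.** There is no plan figure to reproduce. The check is a count from the stated schedule, followed by a search for any text that fills the gap.

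**1. Number of infusions.** Inputs from E1: 2 per week, 4 weeks.

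2 × 4 = 8 infusions. One test precedes infusion 1, so 8 − 1 = 7 infusions (2 to 8) have no stated test before them.

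**2. Days from the only test to infusion 8.** Number the four weeks as days 0–6, 7–13, 14–20 and 21–27, with two different infusion days in each. Infusion 1 then falls on days 0 to 5 and infusion 8 on days 22 to 27.

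- Same two weekdays each week: 3 × 7 + 1 = 22 days to 3 × 7 + 6 = 27 days. This is the more natural reading, because infusions are tied to weekly therapy sessions.
- Weekdays free to move: 22 − 5 = 17 days to 27 − 0 = 27 days.

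The upper end is 27 days either way.

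**3. Effect of one repeat before infusion 5.** Infusion 4 falls on days 8 to 13 and infusion 5 on days 14 to 19.

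| Interval | Weekdays free to move | Weekdays fixed |
|---|---|---|
| First test to infusion 4 | 8 − 5 = 3 to 13 − 0 = 13 days | 7 + 1 = 8 to 7 + 6 = 13 days |
| Second test to infusion 8 | 22 − 19 = 3 to 27 − 14 = 13 days | 7 + 1 = 8 to 7 + 6 = 13 days |

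The longest test-to-infusion gap falls from up to 27 days to at most 13. The longest run of infusions without a fresh test falls from 7 (infusions 2 to 8) to 3 (2 to 4, and again 6 to 8).

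**4. Does other text fill the gap?**

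| Place | Schedules a later pregnancy test? | Says ketamine stops for pregnancy? |
|---|---|---|
| D1, Details of Infusion | No, first infusion only | No |
| D1, incidental findings | No, acts only once something is found | No, discussion and higher care if needed |
| E2, 2.a exclusions | No | By implication, for entry and the first dose |
| E2, 2.d and 2.e withdrawal | No | Not named; an early pregnancy need not meet the grounds |
| F2 and ketamine protocol | No | No |
| G2 | No | No |

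These are schedule counts, not a risk of pregnancy. The documents give no conception rate and no detection delay.

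**The case against.** The strongest reply is that the E2 item does more than bar pregnant people. By its evident intent it also bars those at risk of becoming pregnant, so the group in whom a mid-course pregnancy could arise should be small. This stands, and it narrows the point to screening failure, changed circumstances, and pregnancies not yet detectable at infusion 1. It does not remove the point: E2 is an entry criterion, and D1's advice for the infusion month would be unnecessary if nobody enrolled could conceive.

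A reader might also infer that the plan lets dosing proceed after a positive test. The documents do not support this for the one test that exists. It is done immediately before the first dose and pregnancy is an intended exclusion, so a positive result makes the person ineligible. What is unstated is the action if pregnancy is found later.

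Nor should the E2 wording be read as admitting pregnant participants. Taken literally under an exclusion heading it would exclude people who are not pregnant, but this is a drafting slip and its meaning is plain.

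Two further points are fair. The documents set no testing standard, so infusion 5 is an example and not a derived optimum; a single repeat still leaves infusions 6 to 8 without a fresh test. Also, some relevant text cannot be seen: consent pages were removed, and the safety-ratings table that D1 points to is not identifiable. Either might contain related language, which limits confidence to medium.

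**Conclusion.** The point holds in a limited form. On the visible text, 7 of 8 infusions have no stated pregnancy test before them, the last falling up to 27 days after the only test, and no section says that ketamine stops if pregnancy is found mid-course. The first exposure is already protected by the test together with the intended exclusion.

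This rests on 8 infusions (derived from the schedule; the total is not printed), on two infusions on different days in each week, and on some enrolled participants being able to conceive, as D1's advice implies. It is a safety-procedure point worth correcting. A reader might take the day counts as a measure of risk, or expect a consequence for the trial's results. Neither follows: the counts describe only the schedule, and sample size, power and analysis are unaffected.

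**What to change.** 1. **D1.** Keep the test before infusion 1. For participants able to conceive, add at least one repeat urine test mid-course at an existing infusion visit, for example before infusion 5.
2. **D1.** State that ketamine stops on a positive result at any test.
3. **E2, 2.a.** Delete the opening words 'Not be', so that the item lists pregnancy, or being at risk of it, as a ground for exclusion. Add no new definition of being at risk. That would change eligibility, and whether contraception is required is for the clinical team.

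The cost is a short amendment and, with one repeat, 15 × 1 = 15 extra urine tests at most. It could be as few as 0, because the documents do not say how many of the 15 will be able to conceive. A participant who tests positive before infusion 5 would lose the remaining 4 infusions (5 to 8); each such person is 1/15 = 6.7% of the planned sample. A repeat test finds only a pregnancy detectable by that day, so it reduces the gap without closing it.
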